- Additionally, important medical events that may not result in death, be life-threatening, or require hospitalization may be considered SAEs when, based on appropriate medical judgment, they may jeopardize the patient and may require medical or surgical intervention to prevent one of the outcomes listed in this definition. Examples of such events include allergic bronchospasm requiring intensive treatment in an emergency room or at home, blood dyscrasias or convulsions that do not result in hospitalization, or development of drug dependency or drug abuse.

Clear progression of neoplasia should not be reported as an AE or SAE (unless the investigator considers the progression of underlying neoplasia to be atypical in its nature, presentation or severity from the normal course of the disease in a particular patient). Findings that are clearly consistent with the expected progression of the underlying cancer should not be reported as an adverse event, and hospitalizations due to the progression of cancer do not necessarily qualify for an SAE. In contrast, all deaths including those related to progression of disease and sudden and unexplained death should be reported as an SAE. If there is any uncertainty about a finding being due solely to progression of neoplasia, the finding should be reported as an AE or SAE as appropriate.

Life-threatening, in the context of an SAE, refers to *immediate risk of death* as the event occurred per the reporter. A life-threatening experience does not include an experience, had it occurred in a more severe form, which might have caused death, but as it actually occurred, did not create an immediate risk of death. For example, hepatitis that resolved without evidence of hepatic failure would not be considered life-threatening, even though hepatitis of a more severe nature can be fatal. Similarly, an allergic reaction resulting in angioedema of the face would not be life-threatening, even though angioedema of the larynx, allergic bronchospasm, or anaphylaxis can be fatal.

Hospitalization is official admission to a hospital. Hospitalization or prolongation of a hospitalization constitutes criteria for an AE to be serious; however, it is not in itself considered an SAE. In the absence of an AE, a hospitalization or prolongation of a hospitalization should not be reported as an SAE. This is the case in the following situations:

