6.7 Safety Analyses

Unless specified otherwise, safety analyses described in this section will be conducted for the Safety population, with patients grouped according to whether they received any telaglenastat treatment.

6.7.1 *Exposure of Study Medication*

Study drug exposure status for each component of the study drug, which include treatment duration, total dose received (mg), number of cycles, number of patients with dose adjustment and the reasons will be summarized for each treatment arm for the Safety population.

6.7.2 *Adverse Events*

Verbatim description of AEs will be mapped to Medical Dictionary for Regulatory Activities (MedDRA) preferred terms and system organ classes, and graded by the investigator according to NCI CTCAE v4.03. Treatment-emergent adverse events (TEAEs) will be summarized by mapped term, appropriate thesaurus level, NCI CTCAE grade, and treatment arm. In addition, serious adverse events, severe adverse events

(Grade ≥ 3), and adverse events leading to study drug discontinuation or interruption will be summarized accordingly. These tables will also be presented for TEAEs judged to be related (probably or possibility) to the study treatment. Multiple occurrences of the same event in a given patient will be counted once at the maximum grade. All deaths are reported as SAEs per study conduct. In order to accurately summarize the true SAE rate, all SAE summaries will not count Grade 5 events for patients who died due to progressive disease.

Per protocol and study conduct, safety follow-up is 28 days from date of last study drug administration or until initiation of a new anti-cancer therapy if earlier. For reporting purposes, “treatment emergent” is defined as new adverse events occurring on or after the first dose of study drug is administered until the clinical cutoff date, or existing events that worsened after the first dose during the study.

All listings of adverse events will also include all adverse events.

Deaths reported during the study treatment period and the follow-up period after treatment discontinuation will be listed by treatment arm.

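### SAP 6.7.2 drops Grade 5 events from the SAE tables by the patient's cause of death, whatever the event, and states no matching rule for the TEAE and Grade ≥3 tables

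*SAP*

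**What the plan says.** Protocol 15.1 tells sites that "all deaths including those related to progression of disease and sudden and unexplained death should be reported as an SAE". The same section asks sites not to report clear progression as an adverse event unless it is atypical, but adds a safeguard for doubtful cases: "If there is any uncertainty about a finding being due solely to progression of neoplasia, the finding should be reported".

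SAP 6.7.2 builds on this. It notes that "All deaths are reported as SAEs per study conduct" and, with the aim of showing a true SAE rate, rules that "all SAE summaries will not count Grade 5 events for patients who died due to progressive disease".

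The other summaries in the same paragraph carry no such exclusion. For the main table, "Treatment-emergent adverse events (TEAEs) will be summarized by mapped term, appropriate thesaurus level, NCI CTCAE grade, and treatment arm". Serious events, Grade ≥3 events "and adverse events leading to study drug discontinuation or interruption will be summarized accordingly". The set is then repeated for related events: "These tables will also be presented for TEAEs judged to be related (probably or possibility) to the study treatment". The treatment-emergent period covers "new adverse events occurring on or after the first dose of study drug is administered until the clinical cutoff date".

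Protocol 14.7 plans TEAE and serious-TEAE tables with no exclusion for progression deaths, but SAP section 3 says that the SAP takes precedence on statistical analyses.

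**The concern.** Two separate defects follow from one sentence.

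First, the filter works on the patient. Once a death is attributed to progression, every Grade 5 record of that patient leaves the SAE summaries, whatever its term and whatever the investigator said about relatedness. SAP 6.7.2 does not say who makes the attribution. Yet a named fatal event in such a patient may be one that the site reported precisely because it was not sure that progression was the sole explanation.

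Second, the filter is applied to one family of tables. If progression deaths distort the SAE rate, which is the SAP's own reason for the rule, they distort the any-Grade ≥3 rate in the same way, and that rate is left as it is. It then partly reflects an efficacy outcome.

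Comparing safety and tolerability between the arms is a stated objective (Protocol 5.0), and the cited Phase 1 experience with this combination is 13 patients (Protocol 9.4.1). This trial's arm-by-arm tables are therefore the main comparative evidence on what CB-839 adds to cabozantinib.

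**Working it through.** The plan states no figure to reproduce, so the main check is textual.

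**Step 1. Apply the rule literally.** Take treatment-emergent Grade 5 records and ask which summaries count them.

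| Grade 5 record | Death attributed to progression? | TEAE by grade | Grade ≥3 | SAE | Related SAE |
|---|---|---|---|---|---|
| Progression term, unrelated | Yes | counted | counted | dropped | not applicable |
| Other term, unrelated | Yes | counted | counted | dropped | not applicable |
| Other term, judged related | Yes | counted, also in related TEAEs | counted, also in related events | dropped | dropped |
| Other term, judged related | No | counted, also in related TEAEs | counted, also in related events | counted | counted |

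The SAE column follows from the SAP's words. The TEAE and Grade ≥3 columns are inferred: no exclusion is stated for them. The last two rows differ only in the cause of death, yet one is a related SAE in the tables and the other is not. Since a fatal event is serious by definition (Protocol 15.1), the Grade 5 count should not be higher in the TEAE table than in the SAE table, but under this rule it can be.

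**Step 2. Can the third row occur?** Protocol 15.1 treats death as an outcome and not an event, and Protocol 15.2 asks for a specific diagnosis where feasible, so a Grade 5 record can carry a named diagnosis. The causality guidance in Protocol 15.1 treats an event as at least possibly related unless there is evidence of another cause or no plausible timing. Protocol 11.1.2 lists hemorrhage and GI perforation among the potentially lethal events of cabozantinib. Mixed cases are therefore foreseeable. Nothing in the documents says how frequent they are.

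**Step 3. Scale, under assumptions only.** The documents give no count of progression deaths with a Grade 5 record. Inputs: 208 patients per arm, 416 in total (Protocol 6.0). All percentages below are assumptions.

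- Per arm, if 2% to 10% have a progression-attributed death recorded as Grade 5: 208 × 0.02 = 4.2 and 208 × 0.10 = 20.8, so about 4 to 21 patients per arm for whom the tables disagree.
- If 0% to 25% of those records carry another term: 4.2 × 0 = 0 to 20.8 × 0.25 = 5.2, so 0 to about 5 per arm missing from the SAE tables.
- A second set of assumptions, both arms together: 5% to 10% die of progression within 28 days of the last dose, 416 × 0.05 = 21 to 416 × 0.10 = 42. If 2% to 5% of these also have a separately named fatal event: 21 × 0.02 = 0.4 to 42 × 0.05 = 2.1 events in all.

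**The case against.** The strongest reply is that the rule has a sound purpose. Because every death is entered as an SAE, some records are in the SAE data only for that reason, and removing pure progression deaths from the SAE rate is defensible. That stands. The fault lies in how the rule is specified, not in its aim.

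Nor do the events disappear from the report, as a reader might infer. On the text, they stay in the TEAE-by-grade and Grade ≥3 tables, in the related-event versions of those tables where judged related, in the adverse event listings and in the listing of deaths by arm. Non-fatal SAEs of the same patient still count. This also stands, although a listing does not repair a comparative SAE rate.

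A reader might also size the problem from the 135 deaths expected at the interim OS analysis (SAP Table 3): with 60% to 90% due to progression, 135 × 0.60 = 81 to 135 × 0.90 = 122 patients. The documents do not support this. A death counted for OS is not necessarily a Grade 5 adverse event record. Routine AE and SAE follow-up runs through at least 28 days after the last dose, or to new anticancer therapy if earlier (Protocol 15.2); after that, Protocol 15.3 asks only for SAEs thought possibly or probably related. Some later deaths may still be captured, given the all-deaths instruction in Protocol 15.1 and the SAP's treatment-emergent window to cutoff, but how many is unknown.

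Finally, the claim that progression deaths would mask added toxicity in the Grade ≥3 tables goes too far. Events are tabulated by term, so rows for specific toxicities are unaffected. Only the overall and system-organ-class totals can move, and the overall total only for patients with no other Grade ≥3 event.

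**Conclusion.** The point holds as a defect of specification. SAP 6.7.2 screens Grade 5 events by the patient's cause of death, ignores term and relatedness, and limits the screen to SAE summaries, including related SAEs. A non-progression or related fatal event can therefore be absent from the SAE tables while present in the TEAE tables, and a progression death can count as a Grade ≥3 event with no matching SAE. The first part is explicit in the SAP; the second rests on the absence of a stated exclusion elsewhere.

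The size cannot be derived from the documents. The assumed scenarios give from none to about five lost non-progression events per arm, and zero is within the range. The point affects descriptive safety tables only; no hypothesis test, alpha or power depends on it. It is still worth correcting, because the rule as stated gives comparative safety rates that do not agree with one another.

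**What to change.** Replace the sentence in SAP 6.7.2 with an event-level rule that applies to every table family, along these lines:

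> Grade 5 records are left out of the TEAE, Grade ≥3 and SAE summaries, and of their related-event versions, only if the preferred term denotes progression of the study cancer or death due to it, the record is judged unrelated to study treatment, and it was not reported as atypical progression. Every other Grade 5 event is counted in all of these summaries, whatever the recorded cause of death. A table of deaths by cause and treatment arm is added.

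The relatedness and atypical-progression conditions matter. Without them, the wider rule would remove from every summary the progression reports that Protocol 15.1 specifically asks sites to make. The list of qualifying preferred terms, and the way atypical reports are identified, should be fixed before unblinding.

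The cost is SAP wording, a programming filter and one extra table. A small downside is that the reported fatal SAE count may rise by a few events, some of them terms secondary to progression; the table of deaths by cause lets readers see this.

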14.7 Safety Analysis

Safety will be assessed by the patient incidence and severity of treatment-emergent adverse events (TEAEs). TEAEs are adverse events (AEs) not present prior to protocol treatment, or an already present event that worsens either in intensity or frequency during or following protocol treatment initiation. The analysis will be performed on the Safety Analysis Patient Set as defined in [Section 14.5.2](#).

TEAEs will be coded by System Organ Class and Preferred Term using the Medical Dictionary for Regulatory Activities (MedDRA). The number and proportion of patients reporting a given TEAE will be tabulated by treatment group according to the worst severity reported. Separate tables will be constructed for a) all reported TEAEs, b) serious TEAEs, and c) TEAEs leading to permanent discontinuation of study treatment. The above tables will also be presented for TEAEs judged to be related (probably or possibility) to the study treatment.

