15.2 Recording and Reporting

After informed consent, but prior to initiation of study drug, only SAEs caused by protocol-mandated interventions (e.g., a protocol-required blood test) will be collected.

Patients will be followed for AEs or SAEs from the time the patient initiates treatment with the study regimen through at least 28 days after the last dose of all study treatments (CB-839/placebo and cabozantinib), or until initiation of a new anticancer therapy (if earlier). The Investigator must follow up on all drug-related AEs, SAEs, and other reportable information until the events have subsided, returned to baseline, the patient has initiated any other anticancer therapy, or in case of permanent impairment, until the condition stabilizes.

All AEs and SAEs must be recorded on source documents and collected in EDC system.

Although AEs should be based on the signs or symptoms detected during the physical examination and on clinical evaluation of the patient, a specific diagnosis should be reported as the AE whenever feasible. In addition to the information obtained from those sources, the patient should be asked the following nonspecific question: “How have you been feeling since your last visit?” Signs and symptoms should be recorded using standard medical terminology.

Any unanticipated risks to the patients must be reported by the investigator promptly to the Sponsor and IRB/IEC.

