15.3 Serious Adverse Event Reporting

All SAEs regardless of attribution, other reportable information, and follow-up information must be reported within 24 hr of learning of the event by completing the SAE form and either emailing or faxing the form to the SAE Reporting Contact. Calithera Biosciences (or designee) will process and evaluate all SAEs as soon as the reports are received. For each SAE received, Calithera Biosciences will make a determination as to whether the criteria for expedited reporting have been met. The Medical Monitor should also be contacted for any fatal or life-threatening SAE that is considered possibly or probably related to study drug.

Calithera Biosciences, Inc. (or designee) is responsible for reporting relevant SAEs to the relevant regulatory authorities and participating Investigators, in accordance with FDA regulations *21 CFR 312.32*, *ICH Guidelines*, *European Clinical Trials Directive (Directive 2001/20/EC)*, and/or local regulatory requirements and monitoring the safety profile of the study drug. To meet this requirement, Calithera Biosciences, Inc. (or designee) may request additional information from the sites including, but not limited to, hospitalization records. Any requests for such information should be addressed in a timely manner. Additionally, any SAE considered by an Investigator to be possibly or probably related to the study therapy that is brought to the attention of the Investigator at any time outside of the time period specified for SAE reporting also must be reported immediately to one of the individuals listed on the Sponsor contact information page.

Reporting of SAEs by the Investigator to the IRB/IEC will be done in accordance with the standard operation procedures and policies of the IRB/IEC. Adequate documentation must be maintained showing that the IRB/IEC was properly notified.

PrimeVigilance, the pharmacovigilance vendor, has been contracted to provide drug safety and pharmacovigilance support, including EudraVigilance management and distribution of SUSAR

reports, in relation to CB-839 investigational medicinal product (IMP) clinical development program by Calithera Biosciences Inc.

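### The SAP's treatment-emergent definition runs to the clinical cutoff and progression deaths are excluded only from SAE summaries, so late deaths can count as Grade 5 TEAEs

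*SAP*

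**What the plan says.** **SAP 6.7.2 (Adverse Events)** makes four statements that bear on this point.

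- It describes the window: "safety follow-up is 28 days from date of last study drug administration or until initiation of a new anti-cancer therapy if earlier".
- The next sentence defines treatment-emergent for reporting as "new adverse events occurring on or after the first dose of study drug is administered until the clinical cutoff date", or an existing event that got worse after first dose during the study. Neither part mentions last dose or new therapy.
- It notes that "All deaths are reported as SAEs per study conduct", and for that reason drops Grade 5 events from all SAE summaries when the patient died of progressive disease. No such exclusion is stated for the all-TEAE tables by grade or for the Grade 3 or higher tables.
- Deaths in the treatment and follow-up periods are listed by arm.

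**Protocol.** Section 15.2 collects AEs and SAEs "through at least 28 days after the last dose of all study treatments" (both drugs), with an earlier stop when another anticancer treatment begins. Section 15.1 says "all deaths including those related to progression of disease and sudden and unexplained death should be reported as an SAE"; that sentence has no time limit. Section 15.3 adds that an SAE judged possibly or probably related and "brought to the attention of the Investigator at any time outside of the time period specified for SAE reporting also must be reported immediately". Section 14.7 gives the protocol's own TEAE definition, including "an already present event that worsens either in intensity or frequency during or following protocol treatment initiation", also with no upper limit. SAP section 3 says the SAP's analyses supersede the protocol.

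**The concern.** A treatment-emergent table should show what happened on treatment and shortly after. Under the SAP's wording, the only upper limit is the data cutoff. Whatever reaches the safety database after the 28-day or new-therapy limit is therefore treatment-emergent by definition.

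Deaths are the class of late event most likely to reach it. Survival follow-up continues until death or withdrawal of consent, so late deaths will become known, and the all-deaths rule sends them to SAE reporting. The SAP recognises that progression deaths distort SAE rates and removes them there, but not from the other tables.

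Two things are at stake:

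- Disease deaths long after treatment can inflate the Grade 5 row and the Grade 3 or higher incidence. The SAE and TEAE tables can then give different counts of fatal events.
- If one arm spends longer off treatment before the cutoff, it has more room for such deaths, and the comparison of fatal and severe events partly reflects efficacy.

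**Working it through.** **1. The text, route by route.** Can an event after the window reach the TEAE tables?

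| Route | Basis | Result |
|---|---|---|
| Routine AEs after the window | Protocol 15.2 sets a minimum ("through at least 28 days after the last dose of all study treatments"), but Attachment 1 puts the last visit at 28 (+7) days, and 10.4 collects only survival status and later anticancer therapy | Largely closed |
| Late related SAEs | Protocol 15.3 | Open; keeping them is reasonable |
| Late deaths not due to progression | Protocol 15.1, SAP 6.7.2 | Open in every table |
| Late progression deaths | As above; exclusion limited to SAE summaries | Removed from SAE tables, open in all-TEAE and Grade 3 or higher tables |

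**2. The plan's own figure.** The plan gives no figure for this point. Its PFS inputs are used below, so they were checked first. Inputs (Protocol 14.8): HR 0.69, power 0.85, two-sided 0.05, control median 8 months, 208 per arm, 15 months' accrual plus 7 months' follow-up.

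- Schoenfeld: 4 × (1.960 + 1.036)² / (ln 0.69)² = 4 × 8.978 / 0.1377 = 261 events. Power at 262 events is 0.852.
- Exponential PFS, uniform accrual: event probability = 1 − [exp(−λF) − exp(−λ(A+F))] / (λA), with λ = ln 2 / median. This gives 144.5 + 117.6 = 262.2 events.

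The stated 262 is reproduced.

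**3. How many deaths could fall after the window.** Inputs:

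- SAP 4.2 timing: entry uniform over 16 months, cutoff 8 months later.
- Treatment stops at progression. PFS medians are 8 and 8/0.69 = 11.6 months.
- The window ends w = 28/30.4375 = 0.92 months after progression.
- **Assumption, not in the documents:** post-progression survival is exponential, equal in both arms, with median 8, 12 or 18 months. Protocol 9.1 cites cabozantinib medians of 7.4 months (PFS) and 21.4 months (OS), which suggests this range.

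For a patient with follow-up e, progression rate λ and post-progression death rate μ, the expected time alive beyond the window is

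∫₀^(e−w) λ exp(−λp) · exp(−μw) · [1 − exp(−μ(e−w−p))] / μ dp,

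averaged over e from 8 to 24 months. Deaths after the window = 208 × μ × that mean. For control with median 12: 208 × (ln 2 / 12) × 4.68 = 56.

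| Assumed median (months) | Months alive beyond window, control / CB-Cabo | Ratio | Deaths after window, control / CB-Cabo | Deaths inside window, control / CB-Cabo |
|---|---|---|---|---|
| 8 | 3.94 / 3.11 | 1.27 | 71 / 56 | 11 / 9 |
| 12 | 4.68 / 3.69 | 1.27 | 56 / 44 | 8 / 6 |
| 18 | 5.29 / 4.16 | 1.27 | 42 / 33 | 5 / 4 |

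The formula and a simulation agree to rounding.

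**4. Plausibility.** Total modelled deaths are about 71 + 56 + 11 + 9 = 147 at median 8 and 56 + 44 + 8 + 6 = 114 at median 12. SAP Table 3 expects 135 deaths at the interim OS analysis at about month 25, which lies between these.

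**5. No difference between arms.** With HR = 1 and equal survival, both arms have the same λ and μ, so the extra time and the late deaths are equal in expectation.

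**The case against.** The strongest reply is that the 28-day limit governs collection. Read with the sentence before it, running the definition to the cutoff mostly captures what was collected inside the window. Protocol 14.7 has no upper limit either. Deaths are listed by arm, and progression deaths are already out of the SAE summaries. It is also not settled that a death in long-term follow-up is entered as an SAE: 15.1 has no time limit, but 15.2 sets an SAE window.

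Much of this stands, and it rules out several stronger readings that a reader might infer:

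- **That the SAP replaced a 28-day TEAE rule.** Neither document contains such a rule; the limit is a follow-up and collection window.
- **That events under later anticancer drugs fill the tables.** Follow-up stops at new therapy, so they enter only as a late related SAE or a death.
- **That the tables are unequal by arm and flatter CB-Cabo.** This depends on the arms differing in time off treatment, survival or late reporting.
- **That all calendar time from the window's end to the cutoff measures the problem.** That gives 6.9 against 5.4 months per patient, but it lets patients who have died keep accruing time. Nor is calendar time without AE collection a count of events.

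The reply does not dispose of the deaths. The SAP itself says all deaths are reported as SAEs per study conduct, and a listing does not correct a table.

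**Conclusion.** The point holds in a limited form. The definition has no end tied to last dose or new therapy, and the progression-death exclusion covers one family of tables only. Followed literally, late deaths, including those from progression, can count as Grade 5 TEAEs in the all-TEAE and Grade 3 or higher tables, which can then disagree with the SAE tables.

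The modelled deaths after the window (about 42 to 71 control, 33 to 56 CB-Cabo, of 208 each) are a ceiling on how many could enter. The number that does depends on how many long-term follow-up deaths are recorded as SAEs. The effect on Grade 3 or higher incidence is smaller than on the Grade 5 count, because some of these patients will already have had a Grade 3 or 4 event.

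The ratio of about 1.27 rests on the design HR of 0.69, on treatment stopping at progression and on equal post-progression survival. With equal PFS and survival there is no systematic difference by arm, though disease deaths would still inflate both. The change is worth making before the safety tables are produced. It does not touch the primary analysis.

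**What to change.** In SAP 6.7.2:

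1. Define a TEAE as an event with onset or worsening from first dose through 28 days after the last dose of all study treatment, or until new anticancer therapy, whichever is earlier, plus any later SAE judged related.
2. Apply the exclusion of Grade 5 events for progressive-disease deaths to the all-TEAE and Grade 3 or higher tables as well as to the SAE summaries. The window alone is not enough: the model leaves about 5 to 11 control and 4 to 9 CB-Cabo deaths inside it, and some will be progression deaths.
3. Keep all other later events and deaths in the listing by arm.

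The cost is a sentence or two and a date filter on data already collected. The small downside is that late unrelated events move from tables to a listing.
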